9.9 Health-Related Quality of Life (HRQOL) Analysis

The study design is to prospectively analyze the QOL among patients with stage III NSCLC randomized between standard radiotherapy (60 Gy) versus hypofractionated IGRT radiation therapy. While hypofractionation is hypothesized to yield greater tumor cell kill, it may also increase the normal tissue toxicity, in which case there may be a decrease in HRQOL. The primary normal tissue toxicities in patients receiving radiation for lung cancer are esophagitis and pneumonitis. Prior studies have demonstrated that the most sensitive and clinically meaningful method for accurately capturing the normal tissue toxicities is via patients reported outcomes (PROs), such as HRQOL.

In this randomized trial, we plan to assess the FACT-TOI in all arms at 4 specific

time points to minimize patient burden: baseline (pretreatment), at the end of treatment (last day of treatment), and at the 6 and 12 month follow ups (See Appendix II). In order to analyze the difference in QOL between all arms, we plan to use a brief, validated instrument that is user friendly and has clinical relevance (the Lung Cancer Subscale of the FACT-TOI). FACT-TOI is a measure that sums the functional well being (FWB), physical well being (PWB), and the lung cancer subscale (LCS) of the Functional Assessment of Cancer Therapy - Lung (FACT-L) QOL instrument, which has been extensively used for measuring QOL in patients with lung cancer.[31] In a review of the literature reported that the FACT-L scale has been used in more than 5,000 patients and has been found to be sensitive to changes in performance status, treatment response.[32] FACT has been translated into 26 languages and is available free of charge to institutions with the completion of an agreement to share data, accessible at

http://www.facit.org/translation/licensure.aspx. The full FACT-L questionnaire can be completed in less than 10 minutes. This instrument has not only been shown to be prognostic for survival, but also sensitive to changes in QOL on serial evaluations throughout treatment. Importantly, the FACT-TOI has been associated with clinically meaningful changes in

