patients with lung cancer.[33] The lung cancer sub-scale (LCS) consists of 9 items, involving lung cancer specific symptoms. All items are rated on a 5 item (point) Likert Scale, from 0 (not at all) to 4 (very much). It has been determined that a 3-point difference on the FACT-G subscales is associated with a meaningful difference in clinical and subjective indicators. Thus, a difference of 3 LCS points will be considered clinically significant. As the LCS focuses on lung cancer

symptoms, this will be used for the primary endpoint; however, the more general subscales of physical and functional well-being (on the brief FACT-TOI) will also be collected. See Appendix VIII for the appropriate forms.

In addition, the EQ-5D health related quality of life questionnaire will be used as well. EQ-5D is a standardized instrument for use as a measure of health outcome. Applicable to a wide range of health conditions and treatments, it provides a simple descriptive profile and a single index value for health status. The US version of the EQ-5D will be used, to enable mapping of general HR-QoL scores from EQ-5D scores into health state utility scores (ranging from 0 to 1) for the US population. These utility scores are needed for cost-utility analysis (estimates of costs per "quality adjusted" life-year gained). See Appendix IX for the appropriate forms.

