11.0 Statistical Considerations

11.1 Study Endpoints

11.1.1 Primary Endpoint: Overall survival (Failure: death from any cause)

11.1.2 Secondary endpoints:

11.1.2.1 Quality of Life (QOL) as measured by the Functional Assessment of Cancer Therapy Lung subscale (FACT-L)

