11.5.1 Overall Survival

Overall survival time will be estimated using the Kaplan-Meier approach. The stratified log-rank test will be used to test for a statistically significant difference in survival distributions. The null and alternative hypotheses are H_0 : $S_1(t) < S_2(t)$ vs. H_A : $S_1(t) \ge S_2(t)$, where $S_i(t)$ is the distribution of overall survival times for patients in arm i.

The Cox proportional hazard regression model will be used to determine hazard ratios and 95% confidence intervals for the treatment difference in overall survival. Unadjusted ratios and ratios adjusted for stratification variables and other covariates of interest will be computed.

11.5.2 Quality of Life (Functional Assessment of Cancer Therapy-L):

Patient-reported functional status will be assessed with the lung cancer subscales of the Functional Assessment of Cancer Therapy-Lung (FACT-L). The FACT-L is a 36-item questionnaire that uses 5-point Likert-type response choices (0 = not at all; 1 = a little bit; 2 = somewhat; 3 = quite a bit; 4 = very much). It will take less than 10 minutes to complete the questionnaire. The Trial Outcome Indices (TOI) also will be utilized to measure the summed functional well-being, physical well-being, and the additional concerns (lung symptom module) subscales of the FACT-L. A 5-point deterioration in the FACT-L TOI between pre-treatment and at year 1 will be considered clinically significant. The patient-reported endpoint will be a difference in the deterioration from the pre-induction FACT-L TOI score to the score at 6-month post-treatment. This score measures functional status and a difference of 5 FACT-L TOI points will be considered clinically significant.[33]

The first analysis of change in QOL from baseline to 6 months will only be performed on patients who are still alive at 6 months. Changes in QOL will be also analyzed using all available data at baseline, 6, and 12 months with generalized estimating equations (GEE). We will also compare the percentage of patients in each arm with an effect size for the change in FACT-L TOI scores between pre-induction and 6 months of < .2; this will allow us to compare the percentage of patients in each arm whose functional status remains more similar to baseline levels.

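### Section 9.9 makes the lung cancer subscale (3 points, no time point) the main quality-of-life endpoint, while 11.5.2 makes it the FACT-L TOI change to 6 months (5 points)

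*Combined protocol and SAP*

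**What the plan says.** Overall survival is the trial's primary endpoint, and QOL is one of the secondary endpoints. Three sections define the QOL endpoint:

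- **Section 11.1.2.1 (endpoint list):** "Quality of Life (QOL) as measured by the Functional Assessment of Cancer Therapy Lung subscale (FACT-L". It gives no time point and does not mention the TOI.
- **Section 9.9:** because the LCS concentrates on lung cancer symptoms, "this will be used for the primary endpoint". It adds: "a difference of 3 LCS points will be considered clinically significant". Physical and functional well-being, the other two parts of the TOI, are to be collected as well. Assessments are scheduled at "baseline (pretreatment), at the end of treatment (last day of treatment), and at the 6 and 12 month follow ups", but none of these times is attached to the LCS endpoint.
- **Section 11.5.2:** it opens with the lung cancer subscales and introduces the TOI as an additional measure. It then states: "The patient-reported endpoint will be a difference in the deterioration from the pre-induction FACT-L TOI score to the score at 6-month post-treatment". The sentence after that attaches a 5-point difference to this score. Just before the endpoint sentence stands a separate criterion: "A 5-point deterioration in the FACT-L TOI between pre-treatment and at year 1 will be considered clinically significant".

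The rest of 11.5.2 points to 6 months. The first analysis is the change from baseline to 6 months in patients alive at 6 months. The effect-size comparison also uses 6 months. The 12-month data enter through an additional GEE analysis.

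**The concern.** Sections 9.9 and 11.5.2 each give the lead role in QOL to a different score, with a different meaningful difference, and only one of them fixes a time. An analyst who follows 9.9 reports the LCS against 3 points at a time of their choosing. An analyst who follows 11.5.2 reports the TOI at 6 months against 5 points. Both could cite the protocol.

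The choice can matter. The LCS is only one part of the TOI, so the arms could differ on one and not on the other. Section 9.9 itself says that hypofractionation may increase normal-tissue toxicity and so lower QOL, which makes this endpoint relevant to judging the experimental arm. If the lead measure is settled only after results by arm are known, the QOL conclusion may depend on which result looks better.

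**Working it through.** The documents give no QOL sample size, power, standard deviation or significance level, so there is no QOL figure of the plan's own to reproduce. The check is a comparison of the text, followed by an illustration of size.

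**1. The definitions side by side**

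| Place | Measure | Time | Meaningful difference | How it is labelled |
|---|---|---|---|---|
| 9.9 | LCS | none given | 3 points | primary endpoint (within QOL) |
| 11.5.2, endpoint sentence | TOI change, compared between arms | baseline to 6 months | 5 points | patient-reported endpoint |
| 11.5.2, year-1 sentence | TOI deterioration | baseline to year 1 | 5 points | clinically significant change, not called an endpoint |
| 11.1.2.1 | lung subscale of FACT-L | none given | none given | secondary endpoint |

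The first two rows conflict on measure and on meaningful difference, and the first lacks a time. The last row cannot decide between them. Counting only what the text itself calls the endpoint gives **two contrasts**.

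**2. Can the two measures diverge?**

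Item counts are from the worksheet in Appendix VIII: physical well-being 7, functional well-being 7, lung cancer items 9.

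- TOI items = 7 + 7 + 9 = 23.
- TOI items outside the LCS = 23 − 9 = 14.

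So 14 of the 23 items do not enter the LCS. The scores will be correlated but are not interchangeable.

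**3. What an open choice between two contrasts would mean**

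Assumptions, none of them in the documents: each contrast is tested two-sided at 0.05, the two statistics are bivariate normal under no effect, and their correlation ρ is 0.5 to 0.8.

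P(at least one false positive) = 1 − P(|Z₁| < 1.96 and |Z₂| < 1.96)

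| ρ | P(both inside ±1.96) | P(at least one false positive) |
|---|---|---|
| 0 (upper reference: 1 − 0.95²) | 0.9025 | 0.0975 |
| 0.5 | 0.909 | 0.091 |
| 0.7 | 0.917 | 0.083 |
| 0.8 | 0.922 | 0.078 |

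Over the assumed range the result is about 8 to 9%, some 3 to 4 percentage points above the nominal 5%. Because the LCS is contained in the TOI, independence is not realistic and 0.0975 serves only as a reference.

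**The case against.** **The analysis section is coherent on time.** Section 11.5.2 names one time for its endpoint, and its first analysis and effect-size comparison agree with it. This stands: within 11.5.2 the intended contrast can be read as TOI at 6 months. It does not remove the competing label in 9.9, and nothing in the plan says which section governs.

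**QOL is secondary.** Overall survival is primary and is the basis of the sample size. No alpha is claimed for QOL, and listing it first among the secondary endpoints creates no stated hierarchy. This also stands, and it limits the consequence to the QOL conclusion.

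**Different thresholds on different scales are not in themselves a contradiction.** That is correct. Three points on a 9-item subscale and 5 on a sum that contains it can both be sensible. The conflict is over which measure leads. A reader might also compare 3/36 = 8.3% with 5/92 = 5.4% of the scale range and infer that one threshold is stricter. The documents do not support this. Strictness depends on standard deviations, which are not given. The 36-point range is not fixed either, because the smoking-regret item applies only to patients who have ever smoked.

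**A reader might infer four rival endpoints.** Crossing LCS and TOI with 6 months and 1 year gives four tests, and a false-positive chance of roughly 11 to 16% under the same assumed correlations. The text does not support that count. It assigns neither time to the LCS, and the year-1 sentence states when a deterioration counts as clinically significant without naming a between-arm test.

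**Conclusion.** The conflict is real but narrower than a quick reading of 11.5.2 suggests. Two contrasts are each labelled the main QOL endpoint: the LCS with 3 points and no time in 9.9, and the TOI change to 6 months with 5 points in 11.5.2. The endpoint list leaves the matter open, and the year-1 TOI criterion has no stated role.

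The size of about 8 to 9% is an illustration. It rests on 0.05 per test and a correlation of 0.5 to 0.8, and on the QOL claim being made if either contrast is significant. The case for correction does not depend on that figure: with two incompatible definitions in one document, neither result can be shown to be the one planned.

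This should be corrected. It has no bearing on the overall survival analysis.

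**What to change.** Name one measure, one time point and one meaningful difference, in the same terms, in 9.9, 11.1.2.1 and 11.5.2.

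**Default.** Use the between-arm difference in FACT-L TOI change from baseline to 6 months after treatment, with 5 points as the meaningful difference. This follows the endpoint sentence, the first analysis and the effect-size comparison of 11.5.2. Then:
- in 9.9, remove the primary-endpoint label from the LCS and describe the LCS, with its 3 points, as supportive;
- in 11.1.2.1, name the TOI and the 6-month time point;
- in 11.5.2, state that the year-1 TOI deterioration is supportive.

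**Alternative.** Section 9.9 gives a reason for the LCS, namely its focus on lung cancer symptoms. If the sponsor prefers it, give it a time point, carry it into 11.1.2.1 and 11.5.2, and make the TOI supportive.

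In either case, make and document the decision before QOL data are compared by arm.

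**Cost.** Wording only. The full FACT-L is already collected at baseline, end of treatment, 6 and 12 months, so no visit, item or patient is added. The measure not chosen loses its lead status.

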11.1.2.4 Toxicity: Grade 3-5 adverse events as graded by CTCAE v 4.0

11.2 Sample Size Determination

The sample size calculation is based on the primary endpoint, overall survival at 1 year, and the assumption that patients are randomized until the end of accrual. The sample size is calculated with the 2-sided significance level of 0.05 and 80% statistical power using a 2-sample log rank test. We assume that the overall survival function follows an exponential distribution for each arm. Accrual to the study is assumed to be uniformly distributed. The null hypothesis is that the there are no difference in 1-year survival rates between two arms. We assume that the patients will be accrued for 2 years with a 1-year follow-up. We hypothesize that the patients randomly assigned to the control arm and experimental arm have a 1-year survival rate of 45% (hazard rate [λc]) of 0.799) and 60% (hazard rate [λe]) of 0.511), respectively, which is translated to the hazard ratio of $\lambda e/\lambda c = 0.640$. One interim analysis and a final analysis are planned for early stopping for efficacy. The efficacy testing is based on the Lan-DeMets spending function, which resembles the O'Brien-Fleming boundary. The total sample size of 226 patients (113 in the control arm and 113 in the experimental arm) will be accrued to achieve the desired 80% statistical power and 2-sided significance level of 0.05. Guarding against ineligibility or lack-ofdata rate of up to 5%, the final targeted accrual for this study will be 238 patients (119 per arm). Sample size was estimated using the sample size software EaST version 5.

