11.5.4 Quality-Adjusted Survival Time

The quality-adjusted survival time estimates need to account for the presence of censoring. Due to the induced informative censoring problem, the ordinary survival method (e.g.,

Kaplan-Meier estimator) cannot be applied in this case.[35-37] Accordingly, we will use the inverse-probability weighted method of Zhao and Tsiatis to carry out the survival time analysis.[35, 36] To estimate quality adjusted survival time, data from EQ-5D will first be translated into utility measures. These measures are obtained at discrete time points, so they will be interpolated into the time intervals between the visits. The quality-adjusted survival time is just an integration of the utility measures over a patient's survival time, or until the time limit similar as the cost calculation, whichever occurs earlier.

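### The 6-month quality-of-life comparison and quality-adjusted survival name no adjustment for the baseline values already collected, which costs some precision and leaves both open to chance baseline imbalance

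*Combined protocol and SAP*

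**What the plan says.** Section 11.5.2 defines the outcome as a between-arm difference in change: "The patient-reported endpoint will be a difference in the deterioration from the pre-induction FACT-L TOI score to the score at 6-month post-treatment". It adds that "a difference of 5 FACT-L TOI points will be considered clinically significant". Three analyses follow: the change to 6 months in patients alive at that time, a GEE analysis of the baseline, 6- and 12-month scores, and the percentage of patients in each arm with a small effect size for change. No baseline covariate is named for any of them, and nothing says that the GEE treats the arms as having a common baseline mean.

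Section 11.5.4 says of the EQ-5D outcome: "The quality-adjusted survival time is just an integration of the utility measures", taken to death or to the time limit used for costs, which Section 11.5.3 sets at 2 years. Inverse-probability weighting handles censoring. Baseline utility is not mentioned as a covariate.

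Covariate-adjusted hazard ratios are planned for overall survival (11.5.1) and for progression-free survival and local progression (11.5.6). Section 9.9, the data table in Section 10.0 and Appendix II show that FACT-L and EQ-5D are both obtained before treatment.

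**The concern.** Subtracting the baseline score is not the same as adjusting for it. Because of regression to the mean, an arm that starts higher by chance tends to deteriorate more. A change-score comparison keeps that effect in the treatment contrast and is usually less precise than a model for the 6-month score with baseline as a covariate. In quality-adjusted survival the imbalance works in the other direction: an arm that starts with higher utility tends to accumulate more quality-adjusted time, and this passes into the denominator of the cost-utility ratio.

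Quality of life and cost effectiveness are named secondary objectives, and no sample size or power is given for either. The 6-month analysis also loses the patients who have died, so the remaining information is worth using well.

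**Working it through.** **The plan's own figure.** Section 11.2 says "The sample size is calculated with the 2-sided significance level of 0.05 and 80% statistical power using a 2-sample log rank test", with 1-year survival of 45% and 60% (hazards 0.799 and 0.511, ratio 0.640) and "We assume that the patients will be accrued for 2 years with a 1-year follow-up". The Schoenfeld formula gives 158 events. The event probabilities are 0.775 and 0.624, mean 0.700, so 158/0.700 = 225.8, or 226. Then 226/0.95 = 237.9, or 238. Both stated figures reproduce. They concern overall survival only.

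**Patients left at 6 months.** Taking 6 months from enrollment, 113 × √0.45 = 76 control and 113 × √0.60 = 88 experimental, before any missing forms.

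**Precision of the 6-month TOI comparison.** The documents give no SD and no baseline-to-6-month correlation (rho), so both are assumptions. With a common SD s at the two times:

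- variance of a change score: 2s²(1 − rho)
- variance after baseline adjustment: s²(1 − rho²)
- ratio: (1 + rho)/2

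| rho | ratio | reduction | extra patients needed by the change score |
|---|---|---|---|
| 0.4 | 0.70 | 30% | 1/0.70 − 1 = 43% |
| 0.5 | 0.75 | 25% | 33% |
| 0.6 | 0.80 | 20% | 25% |
| 0.7 | 0.85 | 15% | 1/0.85 − 1 = 18% |

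With 76 and 88 patients and an assumed SD of 15, power for 5 points rises from 56% to 69% at rho 0.5, and from 78% to 84% at rho 0.7.

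**If the SDs differ.** Let the 6-month SD be k times baseline. The ratio becomes k²(1 − rho²)/(1 + k² − 2·rho·k). For k = 1.3:

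- rho 0.4: 1.69 × 0.84/(2.69 − 1.04) = 1.420/1.650 = 0.86, a 14% reduction
- rho 0.7: 1.69 × 0.51/(2.69 − 1.82) = 0.862/0.870 = 0.99, a 1% reduction

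**Chance imbalance in TOI.** With equal SDs, each point by which an arm starts higher adds 1 − rho points to its deterioration. The standard error of the baseline difference among survivors is √(1/76 + 1/88) = 0.157 SD, or about 2.4 points at SD 15. One such imbalance moves the result by about 1.2 points at rho 0.5, or 0.7 at rho 0.7, against the 5-point threshold.

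**Whether the GEE already solves this.** With simulated complete data, a GEE with a full arm-by-time model and baseline as an outcome gave the same 6-month contrast as the change score to rounding error. At rho 0.5 its sampling SD was 0.148 (in SD units), against 0.129 for the baseline-adjusted linear model. With the baseline means constrained equal it was 0.128. The answer therefore depends on a model choice that the text does not state.

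**Quality-adjusted survival.** This was checked by simulation over 2 years with the plan's hazards. The assumptions were mean utility 0.7, SD 0.15 or 0.25, correlation between successive utilities 0.4 to 0.8, no censoring, and baseline utility either unrelated to survival or lowering the hazard by a factor exp(−0.3) = 0.74 per SD.

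- Shift from a one-standard-error baseline imbalance: 0.009 to 0.025 QALY with no link to survival, and 0.024 to 0.039 with one.
- Standard error of the arm difference: 0.069 to 0.080 QALY.
- Variance reduction from adjustment: 2% to 24%.

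The simulation left out the end-of-treatment EQ-5D, so it gives the baseline value somewhat too much weight; the shifts are best read as upper values.

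**The case against.** The strongest reply is that the plan is silent rather than wrong. Section 11.5.2 names an endpoint and no model for the first analysis. A linear model for change with baseline as a covariate gives the same arm estimate as one for the 6-month score with baseline as a covariate, so a change endpoint does not exclude adjustment. This stands: the point is that adjustment is not named, not that it is ruled out. A reader might also infer that the quality-of-life plan makes no model-based use of baseline at all. The GEE contradicts that, although as worded it need not recover the lost precision.

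A second reply is that the gain in TOI precision depends on assumptions. That also stands. The 30% to 15% range needs equal SDs and can nearly vanish without them. In large samples, however, the adjusted estimate is never less precise than the change score.

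A reader might infer a larger effect on the cost-utility result. At an assumed utility SD of 0.20 to 0.25, the standard error of the baseline difference is SD × √(2/113) = 0.027 to 0.033. Carried undiminished over about 1.1 years this is 0.03 to 0.04 QALY, or 16% to 21% of an implied gain of 0.18 (0.254 restricted years at utility 0.7). The documents do not support that as the expected size. It takes baseline differences to persist in full, and they give no correlation. With tracking of 0.4 to 0.7 the same sum is about 0.012 to 0.026, and the simulation comes near 0.04 only when strong tracking is combined with a link between utility and survival. The fair yardstick is also the standard error.

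Finally, heavy attrition is not itself an argument for adjustment: the variance ratio does not depend on the number of patients, and adjusting does not remove the selection of 6-month survivors.

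**Conclusion.** The point holds as a matter of efficiency and specification in secondary outcomes. A reader might take the missing adjustment to mean that the results would be biased. In the full randomized sample neither unadjusted estimator is biased over repeated randomization; what is lost is precision and protection against imbalance in the one trial that is run. Among 6-month survivors baseline differences may not be pure chance, and adjustment is not a cure for that.

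For TOI, the loss is worth correcting if the SDs are similar at the two times and small if the 6-month SD is clearly larger. For quality-adjusted survival the effect is modest: a one-standard-error imbalance shifts the result by between one eighth (0.009/0.069) and one half (0.039/0.080) of its standard error. All SDs, correlations and utility parameters are assumptions. The primary analysis and the 226 patients do not change.

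**What to change.** - **Section 11.5.2, 6-month comparison.** Estimate the arm difference in 6-month TOI from a linear model with baseline TOI and the stratification factors as covariates. The result stays on the TOI scale, so the 5-point criterion applies unchanged.
- **Section 11.5.2, GEE.** Choose one of two forms: keep baseline as an outcome and constrain its mean to be equal across arms, or model only the 6- and 12-month scores with baseline TOI as a covariate. Adding baseline as a covariate while it also remains an outcome row would be mis-specified.
- **Section 11.5.4.** Add an inverse-probability-weighted regression of quality-adjusted survival on arm and baseline EQ-5D utility, and report it with the planned weighted estimate.
- **Baseline.** State which assessment serves as baseline; the endpoint sentence calls it pre-induction, but the protocol describes no induction phase.

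No new data are needed. The cost is a change of wording and a little extra analysis work, mainly for the weighted regression. It should be settled before outcome data are compared by arm, so that adjustment cannot look like a choice made on the results.
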